Once parents completed the informed consent which confirmed their participation in the study and income proxy screener (i.e., public assistance services utilized and parent education), children were randomly allocated at a 1:1 ratio to either control (i.e., summer as usual) or intervention (i.e., free SDC), stratified by public assistance services used/received within family units, grade, and gender. Where parents had two or more eligible children, siblings were grouped together to ensure siblings were randomized to the same condition. Children were allowed to participate in the study for a single summer. Randomization occurred prior to baseline assessments each May. The decision to randomize at this time was made to treat the participating families with dignity and be respectful of their needs in making alternative summer care arrangements if their child was not randomized to receive free SDC. Randomization was performed by a co-investigator ([name]) external to the day-to-day conduct of the trial using a stratified random number generator in STATA (StataCorp LLC, v.18.0). The lead investigator ([name]) and data collectors were blinded to allocation.

Intervention and Control Conditions.

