Food and Beverage Consumption. Children's food/beverage consumption was obtained via parent-reported daily diaries for 14 days during the spring (April/May) and 14 days during summer (July). Weekend days were excluded in analyses as the intervention was only delivered on weekdays. Within the daily diaries, parents completed a modified version of the 2009-2010 National Health and Nutritional Examination Survey (NHANES) Dietary Screener Questionnaire (DSQ).¹² The DSQ is a 26-item food frequency questionnaire in which parents report the frequency of foods/beverages consumed by their child each day, including fruits and vegetables, dairy/calcium, sugar-sweetened beverages, sweets/desserts, whole grains, red meat, and processed meat. For this study, questions on meat were excluded as there is no strong association between meat consumption and childhood obesity, while a question around snacks/chips was added to best reflect the diet of children.¹³ Parents

were sent the daily diary at 8:00pm each day and were asked to complete this with their child to report on what their child ate and/or drank that day. Unlike the original screener, which asked respondents about consumption over the past 30 days (e.g., 1 time last month, 2 times per week), only response options referring to the frequency of consumption for that day were included (e.g., 1 time today, 2-3 times today) to capture day to day variation in consumption of each food/beverage component. For foods items, response options were “none”, “1 time per day”, and “2 or more times per day”. For beverages, the response options were “none”, “1 time per day”, “2-3 times per day”, “4-5 times per day”, and “6 or more times per day”. Procedures for assessing daily food/beverage consumption used in this study were similar to previous investigations with similar populations.¹³ During analysis, response options were collapsed and recoded as did eat/consumed or did not eat/did not consume.

Child and Parent Demographics.

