Sample size calculations were based on the ability to detect a statistically significant group (intervention vs control) by time (before summer to end of summer) difference in the change in zBMI with a mixed-effects model with statistical power of 0.80 and an alpha of 0.05. Estimates from the largest and most recent studies¹⁵⁻¹⁷ conducted to date reported the average change in zBMI during the summer ranged from 0.04 to 0.09, and the average change in zBMI during the school year was -0.02. Accounting for the intraclass correlation at the school level¹⁸ and an anticipated attrition rate of 25%, the total number of children required to be enrolled at baseline was 420 to arrive at a final sample of 330 (165 per condition).

Statistical Analyses.

BMI. The primary analysis was intent-to-treat (ITT), defined as using all available data from children according to the original group they were randomized (free summer day camp or continue summer as usual) regardless of their attendance at a summer program. Analyses used mixed-effects models, accounting for the nesting of repeated measures within children, families (i.e., siblings), and schools. The treatment effect of interest was the group (intervention vs control) and time (pre summer vs post summer) interaction. Missing data on the primary outcome (zBMI) was accounted for using full information maximum likelihood estimation, allowing for all children's zBMI data to be used regardless of missing zBMI at either pre or post summer. Covariates included in

the model were the child's baseline zBMI, biological sex¹⁹ and age,²⁰ self-reported race/ethnicity,²¹ parent education,²² food insecurity status,²³ and poverty level.²⁴ Missing data on covariates were handled using multivariate multiple imputation of 100 datasets for both continuous and categorical covariates using STATA v18.0 multiple imputation commands. Secondary analyses examined the dose-response of summer program attendance including both the intervention and control groups. These models used each of the three summer program exposure metrics as continuous independent variables (standardized to the percentage of days attended during the week), to examine the impact of the amount of summer programming on changes in zBMI. The assumptions for all models were checked using plots of the estimated residuals, no violations were found.

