MVPA, Screen Time, Sleep. The primary analysis was intent-to-treat (ITT), defined as using all available data from children according to the original group they were randomized (free summer day camp or summer as usual) regardless of their attendance at a summer program (e.g., intervention children never attending the SDC and control children attending some other form of SDC). Analyses used mixed-effects models, accounting for the nesting of repeated measures within children, families, and schools. The treatment effect of interest was the group (intervention vs control) and time (pre summer vs post summer) interaction. Missing data on the dependent variables of interest of MVPA, time spent sedentary, sleep, and screen time were accounted for using full information maximum likelihood estimation,²⁵ allowing for all children's data to be used regardless of missing data at either pre or post summer. Covariates included in the model were the child's biological sex¹⁹ and age,²⁰ self-reported race/ethnicity,²¹ parent education,²² food insecurity status,²³ and poverty level.²⁴ Missing data on covariates were handled using multivariate multiple imputation with the covariates serving as variables to inform the imputation of 100 datasets for both continuous and categorical covariates using STATA v18.0 multiple imputation commands.

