Diet. The primary analysis was intent-to-treat (ITT), defined as using all available data from children according to the original group they were randomized to (free SDC or summer as usual) regardless of their parent-reported attendance at a summer program.²⁷ Mixed effects models were used to account for the nesting of repeated daily measures within children. The analyses examined the odds of consuming different foods/beverages during weekdays in the summer, controlling for school year endorsement of consuming that food or beverage, in the free SDC group compared to summer as usual. During analysis, day-level food/beverage response options (e.g., 1 time today, 2-3 times today) were collapsed and recoded as binary values: 1 = consumed and 0 = did not consume. Analyses excluded weekend days as the intervention was only delivered on weekdays. Missing data for outcome variables were accounted for using full information maximum likelihood estimation, allowing for all children's data to be used regardless of missing data. Covariates included child biological sex, parent education, food security status, the use of assistance services (e.g., SNAP, WIC), and income. Missing data for covariates was handled using multiple imputation of 100 datasets for both continuous and categorical covariates.

Secondary analyses were as-treated, defined as using all available data from children based on their parent-reported attendance at a structured program on weekdays in the summer, regardless of what group they were randomly assigned to.²⁸ This analysis examined the impact of attending structured summer programming, both

as a binary predictor (days children attended vs days not attended) and as categorical minutes attended (30-239min/d or ≥ 240 min/d vs did not attend “zero” minutes [reference group]) on the odds of consuming different food/beverages during weekdays in the summer, controlling for consumption during the school year and all covariates included in the primary analysis. The 30-239min/d grouping corresponds to half-day or shorter programs, while ≥ 240 min/d corresponds to longer than half-day up to full-day programs. The assumptions for all models were evaluated by examining multicollinearity, residual plots, and the distribution of random effects; no violations were found. STATAv17.0 was used to run all statistical analyses

References

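### The intent-to-treat diet model nests days within children only, although siblings were randomised together; if siblings' diets are positively correlated, its standard errors are too small

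*Combined protocol and SAP*

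**What the plan says.** Randomization and Blinding describes 1:1 allocation of children and then adds an exception for families: "Where parents had two or more eligible children, siblings were grouped together to ensure siblings were randomized to the same condition". For a household with more than one enrolled child, the family is the unit of allocation.

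The Statistical Analyses section describes the clustering separately for each outcome:

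- BMI: "Analyses used mixed-effects models, accounting for the nesting of repeated measures within children, families (i.e., siblings), and schools".
- MVPA, Screen Time, Sleep: "Analyses used mixed-effects models, accounting for the nesting of repeated measures within children, families, and schools".
- Diet, primary analysis: "Mixed effects models were used to account for the nesting of repeated daily measures within children".

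The Diet text mentions no family level, school level or family-clustered standard error, and nothing elsewhere in the document adds one. It does adjust for school-year consumption of the same item and for sex, parent education, food security, use of assistance services and income.

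The diet outcome comes from the parent. Under Food and Beverage Consumption, parents "were sent the daily diary at 8:00pm each day and were asked to complete this with their child", for 14 days in spring and 14 days in summer, and only weekdays are analysed.

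**The concern.** A child random intercept handles the repeated diary days of one child. It still treats two siblings as independent, although they are always in the same arm and eat from the same household. When cluster members share an arm, any positive correlation left between them adds to the variance of the group comparison, and a model without that level does not see it.

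At stake are the intervals and p-values of the intent-to-treat odds ratios for foods and beverages. The Diet text describes no multiplicity adjustment that might offset an inflated error rate. The plan is also inconsistent: two sets of outcomes from this randomisation get a family level, the third does not, and no reason is given.

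**Working it through.** **Is there a figure to reproduce?** No. The documents state no sample size, power, intraclass correlation or standard error for the diet analysis. The 330 children (165 per condition) under Statistical Power are the zBMI target and serve below only as a convenient size.

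**Inputs**
- From the documents: siblings allocated together; diet model with a child level only; 14 diary days per period, so 10 weekdays if the days are consecutive.
- Assumed: *p*, the share of children in sibling pairs (the rest singletons); ICC, the sibling correlation of child-level consumption left after covariates; a two-sided 5% test.

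**Design effect.** With family sizes *m*, DEFF = 1 + (Σm²/Σm − 1) × ICC. For *N* children, pairs contribute (pN/2) × 4 = 2pN to Σm² and singletons (1 − p)N. So Σm²/Σm = N(1 + p)/N = 1 + p, and DEFF = 1 + p × ICC.

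**Consequences.** True SE / reported SE = √DEFF. Shortfall of the reported SE = 1 − 1/√DEFF. Actual type I error = 2[1 − Φ(1.96/√DEFF)].

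| p | ICC | DEFF | True/reported SE | Reported SE too small by | Type I error |
|---|---|---|---|---|---|
| 0 | any | 1.00 | 1.000 | 0% | 5.0% |
| 0.1 | 0.3 | 1.03 | 1.015 | 1.5% | 5.4% |
| 0.2 | 0.3 | 1.06 | 1.030 | 2.9% | 5.7% |
| 0.3 | 0.5 | 1.15 | 1.072 | 6.7% | 6.8% |
| 0.4 | 0.5 | 1.20 | 1.095 | 8.7% | 7.4% |
| 0.4 | 0.7 | 1.28 | 1.131 | 11.6% | 8.3% |
| 0.6 | 0.7 | 1.42 | 1.192 | 16.1% | 10.0% |

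At the top of the main range, the true SE is 13% larger than the reported one, which makes the reported one 1 − 1/√1.28 = 11.6% too small.

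**Does the child random intercept repair this?** A simulation fitted a logistic mixed model with a child intercept only to 330 children with 10 binary days each. Pairs were randomised together, there was no treatment effect and there were no covariates. Total random-intercept variance was 2.0 on the logit scale, with 2,000 runs per setting. The Monte Carlo error of a 5% rate is √(0.05 × 0.95/2000) = 0.5 percentage points.

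| Children in pairs | Family share of intercept variance | Empirical SD / mean model SE | Type I error |
|---|---|---|---|
| 0% | – | 0.99 | 4.6% |
| 20% | 0.5 | 1.05 | 6.5% |
| 40% | 0.3 | 1.06 | 6.2% |
| 40% | 0.5 | 1.07 | 6.0% |
| 40% | 0.8 | 1.11 | 7.8% |
| 60% | 0.5 | 1.13 | 8.6% |
| 60% | 0.8 | 1.20 | 10.1% |

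The model SE stayed near 0.178 throughout, while the true SD rose from 0.175 to 0.212. The child intercept does not recover the missing variance.

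**The case against.** **The size is unknown.** This stands. The documents report no sibling count and no family correlation. With no sibling groups the omission is harmless, and with few it is close to harmless.

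**The formula may overstate the effect.** This stands in part. School-year consumption and the largely household-level covariates can absorb some sibling correlation, though nothing shows that they remove it; the zBMI and activity models also adjust for household characteristics and keep the family level. In addition, a given family share of intercept variance is diluted by day-to-day binary noise before it becomes a child-level ICC. With 40% in pairs and a share of 0.5, the simulation gave an SE ratio of 1.07 and 6.0% type I error, against 1.095 and 7.4% from the formula with ICC 0.5.

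**The sentence may be an incomplete summary of what was fitted.** Possible. If so, the text needs correcting; as written, it specifies a child-only structure.

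A reader might also infer more than the documents support:

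- *One parent reported for every sibling.* This is plausible, since consent came from one parent or guardian and parents filled in the diaries, but it is not stated. The point does not need it: joint allocation and a shared household are enough.
- *The missing school level also invalidates the standard errors.* Children and sibling groups were allocated, not schools, so omitting school does not by itself make the SE of the group effect too small.
- *The as-treated diet models are wrong by the same amount.* Attendance there varies by day, so part of the contrast is within child. The design effect above does not carry over, and neither the direction nor the size of the error is established.

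**Conclusion.** The point holds conditionally. As written, the intent-to-treat diet model leaves out the level at which siblings were allocated. With any positive residual sibling correlation, it understates the standard error of the group effect.

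Assuming 20–40% of children in sibling pairs and a child-level residual ICC of 0.3–0.7, the design effect is 1.06–1.28, the reported SE is about 3–12% too small, and type I error is about 5.7–8.3%. These ranges rest wholly on the assumed share and correlation; the true figures could lie below or above them.

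Severity is moderate. It would be tempting to conclude that the trial's main result is compromised. The documents do not support that: the primary outcome is change in zBMI, and that model already includes families and schools. Nor can any particular diet odds ratio be called falsely significant on this evidence.

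**What to change.** In the intent-to-treat diet models, add a family random intercept (days within children within families), or keep the child intercept and use family-clustered robust standard errors. Say in the Diet text which was done, and report the number and size of sibling groups in each arm so that readers can judge how much it matters. If sibling groups turn out to be few, the family variance will be poorly estimated, because singletons carry no information that separates family from child; the clustered standard error is then the safer choice. If a family level was in fact fitted, correcting the sentence is enough.

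Include the family level in the as-treated diet models too, without claiming a known direction of change. A school effect is optional, for consistency with the other outcomes.

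The cost is a refit on data already held and slightly wider intervals.
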